	
to baseline
 
 • To assess the effect of ECP on risk of clinical relapse • To assess the effect of ECP versus corticosteroids on the frequency of gadolinium- enhancing T1 weighted lesions on cranial MRI scans obtained at months 6 and 12 compared to baseline • To assess the effect of ECP versus corticosteroids on interval changes in T2 weighted lesion number and volume at months 6 and 12 compared to baseline. • To assess the tolerability and the safety profiles of ECP versus corticosteroids
Number of Subjects	N=66 subjects (33 per treatment arm)
Study design	
This is a Phase II, open-label, randomized, study of ECP versus pulsed corticosteroids in patients with SPMS. Subjects will be randomized at a 1:1 ratio to receive ECP (study arm) or active treatment with intravenous methylprednisolone pulses (control arm) administered every 4 weeks (1 gram per infusion) for 12 months. All subjects will undergo longitudinal MSFC and EDSS testing at baseline and every 3 months through 2 years (See Section 9.1 for timing of schedule of assessments)).
 
Blood will be collected for immunological testing at baseline, months 3, 6, 9 and 12. Subjects will also undergo neuroimaging with brain MRI at baseline and months 6 and 12 following initiation of treatment

Study endpoints	
Primary: Proportion of subjects with no evidence of disease progression at 2 years, defined as a minimum change from baseline in one or more of the following:
 
 • 20% or greater increase in the timed 25 foot walk • 20% or greater increase in the 9 hole peg test • 1 point or greater increase in EDSS score in subjects with baseline EDSS scores between 3 and 5.5 • 0.5 point or greater increase in EDSS score in subjects with baseline EDSS scores equal to or greater than 6 
Secondary:(1) change in plasma levels of immunological factors and frequencies of IFNγ and IL-17 MBP-specific PBMC at months 3, 6, 9 and 12 compared with baseline; (2) adverse events; (3) MSFC 3 dimensional composite z-score every 3 months through 2 years compared to baseline;

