5. PATIENT WITHDRAWAL AND REPLACEMENT

Patients may withdraw from the study at any time without penalty and for any reason without prejudice to his or her future medical care.

Patients must be withdrawn under the following circumstances:

- The patient withdraws consent
- Pregnancy (see Section 8.2.2.9)
- Unacceptable toxicity including patients on corticosteroids who develop psychosis or aseptic necrosis of the femoral head

Patients may be required to withdraw after discussion with the investigator for the following reasons:

- AE(s)
- At the discretion of the investigator
- Violation of eligibility criteria
- Deviation from the treatment plan specified in the protocol (e.g., incorrect administration of the study drug, failure to attend study visits, etc.)
- The treating physician can withdraw the patient from the study at any time and for any medical reason that he/she deems necessary
- The patient has a right to withdraw at any time, for any medical or other reasons.
- Patients who experience a clinical relapse (defined as neurological event characterized by new or worsening symptoms lasting 48 hours after a stable period of at least 30 days and is considered in the judgment of the investigator to be a clinical relapse). Patients who fail therapy will be off study, and further therapy will be at the discretion of the treating neurologist. The study will not cover any form of therapy after the patient is off study.
- Patients who have interval accumulation of T1 or T2 lesions and/ or gadolinium enhancing T1 lesions on the month 6 MRI scan
- In all cases, the reason(s) for withdrawal, and the primary reason, must be recorded on the case report form (CRF) or similar.

Withdrawn patients will be replaced.

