10.1 Planned Sample Size and Number of Study Centers

It is planned to recruit approximately 66 patients (33 per treatment arm). This is a single center study.

Patients will be randomized on a 1:1 basis to corticosteroids or ECP arm.

Patients randomized to the ECP treatment arm must receive their first treatment within 5 days of the baseline visit.

For the randomization of patients, the investigator will use an Interactive Voice Response System (IVRS). Details can be found in the trial master file. IVRS will assign patients to a treatment group based on the pre-defined randomization list.

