10.2 Efficacy Analyses

10.2.1 Analysis of Primary Endpoint

The primary end point is the proportion of subjects with no evidence of disease progression, as defined below, at Week 52. Intent to treat approach will be used. Progression is defined as a minimum change from baseline in one or more of the following parameters:

- 20% or greater increase in the timed 25 foot walk
- 20% or greater increase in the 9 hole peg test
- 1 point or greater increase in EDSS score in subjects with baseline EDSS scores between 3 and 5.5
- 0.5 point or greater increase in EDSS score in subjects with baseline EDSS scores equal to or greater than 6

The proportion of subjects who have not progressed clinically, based on the above criteria, at Week 52 after initiation of study therapy will be compared between treatment groups using the Chi-square test.

The early drop-outs, including patients who withdraw will be considered as non-responders.

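### Section 5 replaces every withdrawn patient, but the plan does not say how replacements are allocated or reconcile them with an intent-to-treat analysis that counts withdrawals as non-responders

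*Combined protocol and SAP*

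**What the plan says.** Section 5 lists reasons for leaving the study and closes with "Withdrawn patients will be replaced". No time limit, arm rule or analysis rule is attached. Among the reasons under which a patient may be withdrawn are clinical relapse and month-6 imaging: "Patients who have interval accumulation of T1 or T2 lesions and/ or gadolinium enhancing T1 lesions on the month 6 MRI scan". The relapse item adds: "Patients who fail therapy will be off study, and further therapy will be at the discretion of the treating neurologist". Adverse events, treatment deviations and investigator discretion are also listed. Randomisation takes place at the screening visit (Section 9.2.2 and Table 2), so nearly all of these exits come after it.

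For the primary analysis, Section 10.2.1 states "Intent to treat approach will be used" and adds: "The early drop-outs, including patients who withdraw will be considered as non-responders".

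On size and allocation, Section 10.1 says "It is planned to recruit approximately 66 patients (33 per treatment arm"), with 1:1 randomisation, and "IVRS will assign patients to a treatment group based on the pre-defined randomization list". The synopsis gives "N=66 subjects (33 per treatment arm") without the qualifier, and Section 10.4 bases its power statement on the same 66. No withdrawal rate or inflation for withdrawals appears anywhere.

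**The concern.** Under Section 10.2.1 a withdrawn patient already has an outcome (non-responder) and a place in the denominator, so the analysis leaves no vacancy to fill. In its ordinary sense, replacing a patient means putting another in that place. The plan does not say whether the withdrawn patient and the replacement are both analysed, which arm the replacement enters, or how far N may rise above 66.

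This matters because several exit reasons are related to outcome or tolerability, the trial is open-label, and withdrawal is partly discretionary. The people deciding on withdrawal know the arm and the patient's course. Treatment burden also differs: roughly 24 + 16 + 20 + 6 = 66 ECP sessions against 52/4 = 13 infusions, so unequal withdrawal is plausible. If substitution were used to hold each arm at 33, recorded failures would drop out of the primary comparison, in greater number from the arm with more withdrawals.

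**Working it through.** **Inputs from the documents.** 33 per arm; 30% (control) and 60% (ECP) without progression at week 52; one-sided 5%; normal approximation (Section 10.4). Withdrawals count as non-responders (Section 10.2.1).

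**Inputs assumed.** Withdrawal rates, because the documents give none.

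**1. The plan's own figure.** Pooled normal approximation without continuity correction, mean rate 0.45:

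- SE under the null: √(2 × 0.45 × 0.55 / 33) = 0.1225
- SE under the alternative: √((0.30 × 0.70 + 0.60 × 0.40) / 33) = 0.1168
- Power = Φ((0.30 − 1.645 × 0.1225) / 0.1168) = Φ(0.844) = 80.06%

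The stated figure of at least 80% reproduces, with no slack.

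**2. Replacement as substitution.** Suppose the true intent-to-treat rate is 30% in both arms, all withdrawals are failures, and replacements fill their places until 33 non-withdrawn patients per arm are analysed. With withdrawal fraction w, the analysed success rate becomes 0.30 / (1 − w). Exact binomial enumeration of the pooled z test (reject if z > 1.645) at 33 per arm gives:

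| Withdrawal, control v ECP | Analysed rates | One-sided type I error |
|---|---|---|
| none | 30.0% v 30.0% | 5.2% |
| 10% v 10% | 33.3% v 33.3% | 5.0% |
| 20% v 20% | 37.5% v 37.5% | 5.1% |
| 5% v 15% | 31.6% v 35.3% | 9.3% |
| 10% v 20% | 33.3% v 37.5% | 9.9% |
| 10% v 25% | 33.3% v 40.0% | 14.0% |
| 10% v 30% | 33.3% v 42.9% | 20.0% |
| 20% v 10% | 37.5% v 33.3% | 2.3% |

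The bias follows the difference in withdrawal and can go either way.

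**3. Replacement as addition.** If each replacement takes the next list assignment and everyone randomised is analysed, no failure is removed and allocation stays random. N rises above 66. If 30%/60% are rates among patients who do not withdraw, both are multiplied by (1 − d), where d is a common withdrawal rate, and n = 33/(1 − d) per arm:

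- d = 10%: 27% v 54%, n = 37, power 77.3%
- d = 20%: 24% v 48%, n = 42, power 74.8%

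**4. No replacement, 33 per arm, everyone analysed.** Same diluted rates and same formula as in step 1:

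- d = 10%: Φ((0.27 − 1.645 × 0.1208) / 0.1162) = 73.0%
- d = 20%: Φ((0.24 − 1.645 × 0.1182) / 0.1144) = 65.5%

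If 30%/60% already count withdrawals as failures, step 1 applies unchanged and power stays at 80.06%. Section 10.4 does not say which is meant.

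**The case against.** The strongest defence is that every rule can be followed as written without harm. The next enrolled patient takes the next IVRS assignment, all randomised patients are analysed, and withdrawals count as failures. The only allocation rule in the documents is the pre-defined list, with no exception for replacements. An analyst who follows Section 10.2.1 would keep withdrawn patients; if they were dropped, its non-responder rule would have little left to act on. This stands: the benign reading is available, and Section 10.2.1 points towards it.

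A reader might go further and infer that Section 10.1 fixes 33 per arm, so that replacement must either swap out failures or steer new patients to a known arm, with bias either way. The documents do not support that. Section 10.1 says approximately 66, no section requires an arm to be restored to exactly 33, and none sends a replacement to the withdrawn patient's arm.

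It is also fair that the type I error figures depend on assumed, unequal withdrawal with every withdrawal a failure. Not all listed exits are outcome-related: withdrawn consent, pregnancy and eligibility violations appear as well.

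The defence does not supply the missing statement. The benign reading is nowhere written, and the synopsis and Section 10.4 give 66 without a qualifier, which leaves substitution open.

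**Conclusion.** The point holds as an unreconciled rule about who is in the primary analysis. Section 5 replaces without limit; Section 10.2.1 leaves nothing to replace; the synopsis and Section 10.4 size the trial at 33 per arm with no margin. Bias is conditional. Under substitution, with the assumptions in step 2, one-sided type I error is about 9% to 20% when ECP withdrawal exceeds control by 10 to 20 points. It is near nominal when withdrawal is equal and below nominal when control withdraws more. Under list-based addition with everyone analysed, there is no such bias. Because the trial is open-label, the choice between these readings cannot be settled credibly once outcomes are known, so it should be settled in the protocol.

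**What to change.** In Section 5, delete the replacement sentence or limit it to patients who leave before randomisation. Since randomisation is at screening, the second option is close to deletion. In Sections 10.1 and 10.2.1, state that:

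- every randomised patient is analysed in the assigned arm, with withdrawals as non-responders;
- any additional patient takes the next IVRS list assignment and is never directed to the arm of a withdrawn patient;
- enrolment stops at a stated maximum N.

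In Section 10.4, say whether 30%/60% already count withdrawals as failures, and give the power as conditional on a stated withdrawal assumption.

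The drafting cost is a few sentences in an amendment, with no change to treatment or to the withdrawal criteria. The statistical cost arises if no patients are added and 30%/60% are completer rates: power at 33 per arm falls from 80.1% to 73.0% at 10% withdrawal and 65.5% at 20%. Recovering 80% would then take 40 or 49 per arm respectively. If the rates already include withdrawals as failures, power is unchanged.

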6. TREATMENT

6.1 Control Arm: Corticosteroid Treatment

Patients randomized to the control arm will receive corticosteroids in Pulses of 1 gram of intravenous methylprednisolone every 4 Weeks for 52 Weeks.

6.2 Study Arm: Extracorporeal Photopheresis

ECP will administered according to the following schedule:

Study Arm: Weeks 1-8: 3 times per week

Weeks 9-16: Twice per week

Weeks 17-36: Treatment on two consecutive days every 2 weeks (or optionally, one treatment per week)

Weeks 37-43: Once every 2 weeks

Weeks 44-52: Once every 4 Weeks

The CELLEX[®] System are integrated photopheresis systems that are approved in US and Europe, and marked specifically to perform photopheresis. With the CELLEX[®] System, whole blood is drawn from the patient, centrifuged and separated into its components: plasma, white blood cells, and red blood cells. The white blood cells and a portion of the plasma are collected in a separate chamber for treatment. The remaining plasma and red blood cells are returned to the patient untreated. This collection process is repeated over several cycles. The buffy coat suspension of white blood cells is then exposed to a predetermined amount of UVA light (photo activation) after being inoculated with UVADEX[®] (methoxsalen) Sterile Solution. Following the photo activation of the buffy coat suspension, the treated cells are returned to the patient.

Every attempt should be made to process 1500-2000 mL of blood during each treatment.

UVADEX[®] (methoxsalen) Sterile Solution is supplied in a 10 mL single-use vial. Each mL of solution contains 20 mcg of UVADEX[®] (methoxsalen) Sterile Solution. Each vial contains 10 mL of UVADEX[®] (methoxsalen) Sterile Solution, which is more drug than necessary for most treatments. However, the vials are designed for a single use. Therefore, there will be surplus of drug remaining in the vial at the conclusion of each treatment. Study center staff should NOT attempt to reuse any portion of this unused study drug once the seal has been compromised. The remaining UVADEX[®] (methoxsalen) Sterile Solution should be discarded after verification of dose by the study monitor as per study reference manual.

In the ECP process, UVADEX[®] (methoxsalen) Sterile Solution will be injected directly into the Recirculation Bag of the extracorporeal circuit after completion of the buffy coat collection, just prior to initiating photo activation. The dose of UVADEX[®] (methoxsalen) Sterile Solution used to inoculate these cells will be calculated based on the treatment volume collected during the plasma/buffy coat collection process, using the following formula:

Treatment Volume* in mL × 0.017 = Dose of UVADEX[®] (methoxsalen) Sterile Solution (in mL) required for administration into the recirculation bag

*As displayed on the CELLEX[®] System screen

Example: If 240 mL of the treatment volume is collected, the dose administered equals:

- (240 mL) x (0.017) = 4.08 mL
- 4.08 rounded to the nearest tenth is 4.1 mL

Therefore, a dose of 4.1 mL of UVADEX[®] (methoxsalen) Sterile Solution should be administered to the recirculation bag.

After the cells are inoculated with UVADEX[®] (methoxsalen) Sterile Solution, the buffy coat/plasma suspension is irradiated with ultraviolet-A light and then reinfused back into the patient.

For further information, please refer to the Investigator's Brochure.

7. STUDY PRODUCT

7.1 Identity

Extracorporeal Photopheresis procedural kits and UVADEX[®] (methoxsalen) Sterile Solution will be supplied by Therakos, Inc. at no cost. A CELLEX[®] System) must be available for treatment of study patients for the duration of the study.

THERAKOS Photopheresis System

The CELLEX[®] System is an integrated photopheresis systems that are approved in US and Europe, and marked specifically to perform photopheresis.

Patients in the ECP arm will have all of their ECP treatments with the same CELLEX[®] System.

For further information, please refer to the Investigator's Brochure.

In this protocol, UVADEX[®] (methoxsalen) Sterile Solution will be used in conjunction with the CELLEX[®] System. Please refer to the Operator's Manual for complete information and instructions for operating the CELLEX[®] Systems (<https://therakos.com>). The Therakos[®] Photopheresis Systems and kits will be ancillary clinical supplies.

7.1.1 UVADEX[®] (methoxsalen) Sterile Solution

The active ingredient in UVADEX[®] (methoxsalen) Sterile Solution is 8-methoxypsoralen (methoxsalen). Methoxsalen is a naturally occurring photoactive substance found in the seed of the Ammi majus (umbelliferae plant). It belongs to a class of compounds known as psoralens or furocoumarins. The chemical name is 9-methoxy-7H-furo[3,2-g][1]-benzopyran-7-one. The formulation of the drug is a sterile liquid at a concentration of 20 mcg/mL in a 10 mL vial. A complete description of the pharmacokinetic activity of methoxsalen is available in the Investigator's Brochure.

Systemic exposure to UVADEX[®] (methoxsalen) Sterile Solution following ECP is minimal. The total dose of methoxsalen used to inoculate these cells is less than 1/200th of the oral dose used in conjunction with the UVAR XTS[®] System. Plasma levels obtained as part of other clinical studies have shown no detectable level (<10 ng/mL) 30 minutes after the reinfusion of the treated cell suspension containing the UVADEX[®] (methoxsalen) in >75% of patients.

Adverse events associated with the ECPs process during CTCL clinical trials include venous access complications, transient fever and worsening of the underlying CTCL skin rash and transient hypotension associated with hypovolemia. A complete description of the AEs documented in studies using UVADEX[®] (methoxsalen) Sterile Solution is provided in the Investigator's Brochure.

UVADEX[®] (methoxsalen) Sterile Solution is currently approved in the US, UK, Germany, and Austria for use in the palliative treatment of the skin manifestations of CTCL unresponsive to other therapies.

7.2 Packaging, Labeling and Storage

UVADEX[®] (methoxsalen) Sterile Solution is packaged in 10 mL, 13 mm, United States Pharmacopeia Type I borosilicate amber glass vials. The closure is a 13 mm, gray butyl rubber stopper laminated with 0.1 mm fluorocarbon polymer film. A 13 mm aluminum flip-off cap, with a clear lacquer foil and purple plastic flip-off button, is used to seal the stoppered vials.

UVADEX[®] (methoxsalen) Sterile Solution must be stored at between 15°C and 30°C (USA labeling) or less than 25°C (European labeling).

Procedural kits should be stored in a secure location, at room temperature, and labeled with “Clinical Trial Use Only”.

UVADEX[®] (methoxsalen) Sterile Solution will be labeled according to the US regulations, and will be labeled as “Investigational Product”.

Corticosteroids will be obtained from the Pharmacy at the University of Michigan.

7.3 Drug Accountability

7.3.1 Shipment and Receipt

At the time clinical supplies UVADEX[®] (methoxsalen) Sterile Solution and Procedural Kits are received at the University of Michigan, a “Receipt of Investigational Drug/Device” form will be completed. This receipt will include the total number of supplies received, the date received, and the condition of the supplies at time of receipt. This form is to be signed and dated by the staff member appointed by the investigator to account for investigational supplies. The white copy of this form is to be returned to the Therakos clinical department or its designated representative. The yellow copy of the form should be kept at the site and filed with the investigational drug/device log.

In the event that drug or devices do not arrive at the study center by the date indicated on the form or the number of investigational products received at the site does not correspond with the number indicated on the form, Therakos clinical department should be notified immediately.

7.3.2 Accountability Logs

An accurate record of all supplies received and used at the University of Michigan should be maintained and updated regularly. Procedural kit use will be recorded on the Investigational Device Inventory Log. UVADEX[®] (methoxsalen) Sterile Solution use will be recorded on the Investigational Drug Log. In the event that study drug or devices are damaged, an account should be made on the appropriate log.

At the conclusion of the study, all remaining procedural kits must be returned to the Therakos or destroyed at the site according to the clinical monitoring plan. Once all study products have been accounted for and verified by Therakos or its designated agent, unused vials of UVADEX[®] (methoxsalen) Sterile Solution will be destroyed.

7.3.3 Investigational Device

An Investigational device, the CELLEX[®] System, is available at the University of Michigan.

7.4 Compliance

Study drug used, dosage administered, and intervals between visits will be recorded during the study.

7.5 Concomitant Medications

Any medication the patient takes other than the study drug, including herbal and other non-traditional remedies during the 52 Week study, is considered a concomitant medication. All concomitant medications must be recorded in the CRF. The following information must be

recorded in the CRF for each concomitant medication: generic name, route of administration, start date, stop date, dosage, and indication. Any changes in the dosage or regimen of a concomitant medication must be recorded in the CRF.

At Screening, patients will be asked what medications they have taken during the last 30 days and what concomitant medication they are taken. At each subsequent study visit, patients will be asked what concomitant medications they are currently taking.

The following drugs/therapies are permitted at the investigator's discretion:

- Medications to prevent infection (pneumocystis, viruses and fungal organisms, etc.) per institutional practice.
- Venous access for ECP (at investigator's discretion and per institutional practice).
- Systemic steroids may be administered for clinical relapse or the emergence of gadolinium enhancing MRI lesions.

The following drugs/therapies are prohibited during the treatment period of the study:

- Tysabri® (natalizumab) or other intravenous DMA
- Initiation of dalfampridine or change in the dose of dalfampridine within 6 months prior to randomization
- Treatment with any of the medications or procedures listed below:
- Glatiramer acetate, interferon-beta, fingolimod, teriflunomide or dimethylfumarate within 3 months prior to randomization
- Natalizumab within 3 months prior to randomization
- Cyclophosphamide within 1 year prior to randomization
- Mitoxantrone within 1 years prior to randomization
- Rituximab within 6 months prior to randomization,
- Ofatumumab, ocrelizumab, cladribine, daclizumab within 2 years prior to randomization
- Intravenous immunoglobulin within 6 months prior to randomization
- Plasmapheresis within 1 year prior to randomization

Corticosteroids within 3 months prior to screening, with the following exceptions: Topical ointments or creams, or eye drops that contain corticosteroids; Intranasal Steroids or Oral Steroids given in a single dose as a premedication for a procedure such as gadolinium-enhanced MRI.

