3. OVERALL DESIGN AND PLAN OF THE STUDY

3.1 Overview

This is a Phase II randomized, open-label study to evaluate the efficacy of extracorporeal photopheresis (ECP) versus IVMP on disability progression in subjects with SPMS. At the initial screening visit, an extensive medical history will be obtained and a detailed neurological examination will be performed to determine eligibility. Subjects who meet eligibility criteria will be enrolled in one of two study arms. Subjects will be randomized at a 1:1 ratio to receive ECP (study arm) or active treatment with intravenous methylprednisolone pulses (control arm) administered every 4 Weeks (1 gram per infusion) for 52 weeks.

ECP will be administered according to the following schedule:

Study Arm: Weeks 1-8: 3 times per week

Weeks 9-16: Twice per week

Weeks 17-36: Treatment on two consecutive days every 2 weeks (or optionally, one treatment per week)

Weeks 37-43: Once every 2 weeks

Weeks 44-52: Once every 4 Weeks

[figure not shown]
All subjects, including patients who receive corticosteroids, will be evaluated using the MSFC tool at baseline and every 3 months through 2 years (See Section 9.1 for timing of the schedule of assessments). They will also be scored using the EDSS at baseline and every 3 months through 2 years. Subjects in the control arm will be evaluated by MSFC and EDSS during the week prior to their next intravenous methylprednisolone infusion. Blood will be collected for immune function (cytokines) testing at baseline, and months 3, 6, 9 and 12. MRI will be done at baseline as well as months 6 and 12 following initiation of treatment; if the disability measurements are stable or improved at any point in time, then ECP will be continued per protocol..

Patients in the ECP arm should have all of their treatments with the CELLEX[®] System. Patients randomized to the ECP arm must receive their treatment within 5 days of baseline visit.

In the ECP process, UVADEX[®] (methoxsalen) Sterile Solution will be injected directly the recirculation bag of the extracorporeal circuit after completion of the buffy coat collection. The dose of UVADEX[®] (methoxsalen) Sterile Solution will be calculated based on the standard treatment volume formula (See Section 6.2).

For the schedule of assessments, please refer to Section 0.

Figure 1: Study Design

ECP=Extracorporeal Photopheresis MRI: Magnetic Resonance Imaging

¹ Frequency of ECP treatments:

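### After relapse or new MRI lesions, an arm-aware choice between withdrawing and keeping the patient can decide the primary outcome, and the plan gives no single rule for it

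*Combined protocol and SAP*

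**What the plan says.** Section 3.1 describes a randomised, open-label trial. Four provisions bear on a patient who has a relapse or new MRI lesions.

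- **Section 5 (withdrawal).** Apart from a list of mandatory reasons, there is a second list headed "Patients may be required to withdraw after discussion with the investigator for the following reasons". It includes clinical relapse, as judged by the investigator, and, for the month 6 scan, "Patients who have interval accumulation of T1 or T2 lesions" and/or gadolinium-enhancing T1 lesions. The relapse item continues: "Patients who fail therapy will be off study, and further therapy will be at the discretion of the treating neurologist". Failing therapy is not defined. The section ends: "Withdrawn patients will be replaced".
- **Section 7.5 (concomitant medication).** Under the lead-in "The following drugs/therapies are permitted at the investigator's discretion", it says: "Systemic steroids may be administered for clinical relapse or the emergence of gadolinium enhancing MRI lesions".
- **Section 3.1 (continuation).** After the MRI schedule it adds: "if the disability measurements are stable or improved at any point in time, then ECP will be continued per protocol". Methylprednisolone has no matching sentence; sections 3.1 and 6.1 set its pulses at every 4 weeks for 52 weeks.
- **Section 10.2.1 (primary analysis).** The approach is intent to treat, and "The early drop-outs, including patients who withdraw will be considered as non-responders". Progression is defined by the timed walk, peg test and EDSS at Week 52. Relapse, MRI lesions and rescue steroids are not components and have no handling rule.

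**The concern.** For gadolinium-enhancing lesions at month 6, the protocol authorises both removing the patient and treating the patient on study. For new T1 or T2 lesions, withdrawal is optional. For relapse, section 7.5 implies that the patient can stay, while the sentence in section 5 on failing therapy can be read the other way.

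The choice fixes the endpoint. Withdrawal is non-response whatever the patient's disability; retention leaves the outcome open until Week 52. Scoring withdrawals as failures is usually thought conservative, but it is neutral between arms only if the decision to withdraw does not depend on the arm. Here the decision-maker knows the arm, and no independent review of the decision is described. With 33 patients per arm, each reclassified patient moves that arm's rate by 1/33, or 3.0 percentage points.

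The replacement sentence adds a further gap: it does not say whether a replaced patient remains in the intent-to-treat analysis.

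**Working it through.** **The plan's own figure.** Inputs from section 10.4: 30% v 60% without progression, 33 per arm, one-sided 5%. Pooled rate 0.45. Standard error under the null: √(2 × 0.45 × 0.55 / 33) = 0.1225. Under the alternative: √((0.30 × 0.70 + 0.60 × 0.40) / 33) = 0.1168. Power = Φ((0.30 − 1.645 × 0.1225) / 0.1168) = Φ(0.844) = 80.1%. The stated power of at least 80% is reproduced. It does not depend on the withdrawal rule.

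**What happens to one event patient**

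| Path | Text used | Primary outcome |
|---|---|---|
| Withdrawn | Section 5, optional list | Non-responder (10.2.1) |
| Kept, with or without steroids | Sections 5 and 7.5 | Observed Week 52 status; success possible |

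Section 9.2.8 has a withdrawn patient complete the Week 52 assessments at withdrawal, but 10.2.1 still scores that patient as a failure.

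**Illustrative error rate.** The documents give neither event rates nor retention rates, so these are assumptions:

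- no treatment effect, with 30% success in both arms among patients without an event (the control rate in 10.4);
- event proportion e, the same in both arms;
- proportion r of event patients retained: 75% in one arm and 25% in the other, shown here with the higher figure in ECP;
- success s if retained: 30%, or 15% if an event worsens prognosis.

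Success rate in an arm = 0.30(1 − e) + e × r × s. For example, with e = 20% and s = 30%: control 0.24 + 0.20 × 0.25 × 0.30 = 25.5%; ECP 0.24 + 0.20 × 0.75 × 0.30 = 28.5%. Error is the sum of the binomial probabilities of all outcome pairs (33 per arm) for which the uncorrected pooled z exceeds 1.645 in ECP's favour.

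| Events | Control v ECP, s = 30% | Error | Control v ECP, s = 15% | Error |
|---|---|---|---|---|
| 0% | 30.0 v 30.0% | 5.2% | 30.0 v 30.0% | 5.2% |
| 2% | 29.55 v 29.85% | 5.5% | 29.48 v 29.63% | 5.3% |
| 5% | 28.88 v 29.63% | 6.0% | 28.69 v 29.06% | 5.6% |
| 10% | 27.75 v 29.25% | 6.9% | 27.38 v 28.13% | 6.1% |
| 20% | 25.5 v 28.5% | 9.0% | 24.75 v 26.25% | 7.1% |
| 30% | 23.25 v 27.75% | 11.7% | 22.13 v 24.38% | 8.3% |

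With equal retention (50% in each arm) and s = 30%, error stays at 5.2–5.4% across 2–30% events, so the inflation comes from unequal handling and not from the events. If the split is reversed, the two rates swap and error in ECP's favour falls below 5.2%.

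Section 10.2.1 does not state sidedness. Under a two-sided 5% test, error in ECP's favour for s = 30% is 2.8%, 3.1%, 3.6%, 4.8% and 6.4% at 2–30% events, against 2.7% with none.

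**The case against.** **Direction.** A reader might infer from section 3.1 that the plan leans towards keeping ECP patients, so that any bias favours ECP. The documents do not support this. The sentence depends on stable or improved disability, mentions neither relapse nor lesions, and says only that ECP continues as planned. Control pulses are already fixed for 52 weeks and need no matching sentence. Nothing directs earlier withdrawal of controls. The objection stands: the direction is unknown.

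**Discretion after relapse.** If the sentence on failing therapy refers to relapse, relapse compels withdrawal and only the MRI trigger is optional. That trigger is limited to the month 6 scan, and section 8.1.3 has a board-certified neuro-radiologist determine the lesions. This stands in part. The sentence sits in an optional list, its key term is undefined, and section 7.5 allows steroids for relapse, so the text is unclear. For MRI lesions, the decision to withdraw remains with the investigator on either reading.

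**Size.** The 75% v 25% split is assumed. Section 4.1 requires two relapse-free years before screening, so relapses may be rare; MRI event frequency is unknown. At 2–5% events the effect is negligible, and a poorer prognosis after an event shrinks it further. This stands.

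**Estimand.** Counting withdrawal as failure is a recognised rule, prespecified and worded alike for both arms. Using observed Week 52 status instead is partly a choice of estimand, and brings in patients whose later therapy is chosen by the treating neurologist. This stands as a cost, but it does not remove the dependence of the present rule on an arm-aware decision.

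**Conclusion.** The concern holds as a cheap improvement. Followed as written, the plan lets an unmasked decision turn the same clinical or MRI event into a certain failure or a possible success. This is clearest for lesions on the month 6 MRI and uncertain for relapse. Whether the decisions would differ by arm, and in whose favour, cannot be established from the documents.

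Under the assumed 75% v 25% split, one-sided error in favour of the arm that retains more is 5.5–6.0% at 2–5% events and 6.9–11.7% at 10–30% events, or 6.1–8.3% at 10–30% events if retained patients succeed 15% of the time, against 5.2% with no events. The upper figures need both frequent events and strongly unequal handling; neither is documented.

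**What to change.** **Sections 3.1, 5 and 7.5.** State one rule, identical in both arms: relapse or MRI lesions may change or stop treatment but do not by themselves end follow-up. Define or delete the term for failing therapy. Make the section 3.1 continuation sentence arm-neutral or delete it. Keep these patients on the scheduled 3-monthly visits to Week 52. State that replaced patients stay in the intent-to-treat set.

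**Section 10.2.1.** Score patients followed to the Week 52 window (section 9.1: Week 52 ± 1 month) on observed status, and keep non-response for those with no assessment in that window. An early-termination visit before the window should not count as one. Add one sensitivity analysis, the same in both arms, that counts any relapse, rescue steroid use or section 5 MRI event before Week 52 as non-response.

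**Cost.** Mainly wording, follow-up of some off-treatment patients on visits already scheduled, and one extra analysis. Relapses, MRI results and medication indications are already collected. Later therapy dilutes the contrast, and the estimand shifts towards treatment policy. The sensitivity analysis loses power: if events are equally frequent in both arms and unrelated to outcome, the rates become 0.30(1 − e) v 0.60(1 − e), and the section 10.4 formula gives 78.7%, 76.6%, 73.0%, 65.5% and 57.8% at 2%, 5%, 10%, 20% and 30% events, against 80.1%. Relapse still rests on investigator judgement and section 5 still allows withdrawal for other medical reasons, so discretion is reduced but not removed.
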